Face-reader data collection. We have acquired new software (Facereader from Noldus) that can be used to analyze facial expressions from an inputted video and to output emotional experiences resultant from the facial analysis. This software complements the physiological data acquisition that we are doing and can add a new dimension to our data collection and analysis. We plan to video record participant's faces during the stressor and regulation periods of the study using a Microsoft webcam that is connected directly to a Duke approved laptop or computer. We will ask at consent for special permission for this procedure. We will only record participants' faces if consent is given. These recordings will be transferred right away at the end of the session on a secured server and deleted from the laptop (similar procedures as for assessment videos). The videos will be kept up to 6 years post study finish and deleted within that timeframe.

Psychological Functioning: Exploratory outcome variables will be changes in self-reported impairments in daily functioning and other psychiatric symptoms. These include:

1. Difficulties in Emotion Regulation Scale (DERS) (Gratz, 2004)
2. Interpersonal Reactivity Index (IRI),(Davis, 1980)
3. Toronto Mindfulness Scale (TMS) (Lau, et al., 2006),

4. Basic Empathy Scale (BES) (Carre et al., 2013)
5. Patient Health Questionnaire-depression module (PHQ-9) (Kroenke & Spitzer, 2002)
6. Social Interaction Anxiety Scale (SIAS; Mattick & Clarke, 1998)
7. NIH Toolbox Adult Social Relationship Scales (NIH SRS) (Cyranski, 2013)
8. Ambiguous Intentions Hostility Questionnaire (AIHQ-A; Combs et al, 2007)
9. Early Memories Task (EMT; Mayman, 1968)
10. Psychological Flexibility Questionnaire (PFQ; Ben-Itzhak, 2014))

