## Selection of Subjects

Inclusion criteria include

- (1) ages 18-55;
- (2) have a smartphone and agree to receive text-messages;
- (3) high emotion dysregulation, assessed with the Difficulties with Emotion Regulation Scale (DERS)(Gratz & Roemer, 2004). There is no single consensus definition of difficulties with emotion regulation. However, one influential contemporary model proposes a multi-dimensional approach to conceptualizing difficulties with emotion regulation, including difficulties with: emotional awareness, emotional clarity, achieving goals when upset, impulsivity when upset, unwillingness to accept negative affect when upset, and accessing strategies to regulate emotions when upset (Gratz & Roemer, 2004). In the present application, we utilize this model and accompanying measure, the Difficulties with Emotion Regulation Scale (DERS; Gratz & Roemer), when characterizing our sample as being individuals who have problems regulating emotions. The mean DERS total score across all published reports (n = 13) with adult psychiatric samples (n = 19) is 112.15 (SD = 22.38). Following the established protocols from previous studies, we will use a total score of 90 or higher in the DERS for inclusion. In our previous study (Pro000035922), the 208 eligible participants had a mean DERS score of 117.6 (SD=17.95) at intake. These participants met criteria for a variety of affective and personality disorders, including major depression (68.3%, 22.1% current), generalized anxiety disorder (40.4%), and borderline personality disorder (11.1%). Therefore, we are confident that this DERS threshold will ensure recruitment of a transdiagnostic, clinical sample with emotion dysregulation.

Exclusion criteria include

- (1) Current mania;
- (2) Meets criteria for any current psychotic disorder symptom;
- (3) Currently/chronically homeless;
- (4) Current suicidal ideation (see data & safety section for specific criteria);
- (5) Psychiatric hospitalization within past 6 months;

(6) Unable to read, blind or deaf. Our previous study recruited only participants who were currently in treatment, but this study will include both participants who are currently in treatment, as well as those who are not in treatment. Intelligence Quotient (IQ) will be assessed with the North American Adult Reading Test (NART). 21-22 Subjects with a NART calculated IQ score of <90 will be excluded from the study.

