## Data Analysis & Statistical Considerations

For the primary outcome of biases in emotion perception, the estimates were derived from a mean difference between conditions. With a Type-I error rate of 5% and 72 participants (24 per group), we will have at least 80% power to detect a medium to large effect size (Cohen's  $f = 0.38$ ), based on previous research demonstrating negative biases in emotion perception using similar behavioral measures. (Schmid & Schmid Mast, 2010) Because we anticipate a 10% to 15% rate of dropout, 30 participants will be randomized to each group. Therefore, this study will recruit 90 adult participants over the age of 18 who have high emotion dysregulation and interpersonal problems.

Since 2004, the CBTRP has recruited a range of adult psychiatric samples all characterized by problems with emotion regulation. Across studies of emotional functioning, it is estimated that our lab has run over 980 participants since 2004, at a rate of roughly 90 per year. In our previous NIMH project, over 33 months we have screened 1154 individuals and enrolled 169 participants, at a rate of 5.12 per month. We project enrolling 90 participants over 14 months, at a rate of 6.43 per month. Given our demonstrated track record of success meeting the required recruitment target in the present application, we expect to meet recruitment targets in the proposed project.

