differences in the valence of emotion perception ratings over the one-week testing phase. We will also examine whether changes in emotion dysregulation and distress mediate changes in negative biases over time. Finally, we will also explore the effects of the intervention on self-reported psychological and social functioning. Hypothesis 2: One week of hearing the tones via mobile phones will lead to greater long-term changes in negative biases emotion perception for participants in the emotion regulation condition compared to the participants in the control conditions. Changes in emotional regulation and distress over time will mediate changes in negative biases in emotion perception over time.

If our hypotheses are not supported and the conditions do not have significantly different effects on emotion perception, these findings would be indicative of trait-like deficits in emotion perception beyond the momentary effects of mood or perspective-taking. We would then use moderation analyses to explore the role of other stable factors within emotion perception performance, such as trait empathy (measured by the IRI) or psychiatric diagnoses.

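### The plan reads a null result as trait-like deficits and follows it with moderation analyses, whose interaction terms do not test that explanation

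*Combined protocol and SAP*

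**What the plan says.** The last paragraph of Data Analysis & Statistical Considerations, after Hypothesis 2, covers the case where the hypotheses are not supported and the arms do not differ significantly. It first interprets that outcome: "these findings would be indicative of trait-like deficits in emotion perception beyond the momentary effects of mood or perspective-taking". It then gives the next step: "We would then use moderation analyses to explore the role of other stable factors within emotion perception performance", with examples "such as trait empathy (measured by the IRI) or psychiatric diagnoses". It states no model, focal predictor, interaction term, diagnosis coding or multiplicity rule, and it claims no power for this step. The wording marks the step as exploratory.

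The only power statement concerns the three-arm comparison: "With a Type-I error rate of 5% and 72 participants (24 per group), we will have at least 80% power" for Cohen's f = 0.38. On attrition the plan says: "Because we anticipate a 10% to 15% rate of dropout, 30 participants will be randomized to each group".

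Diagnosis rates appear only in Selection of Subjects, for the 208 eligible participants of the previous study: major depression 68.3% (22.1% current), generalized anxiety disorder 40.4%, borderline personality disorder 11.1%. The same section says the earlier study recruited only people in treatment, whereas "this study will include both participants who are currently in treatment, as well as those who are not in treatment".

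**The concern.** Two steps in the paragraph do not connect.

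First, a non-significant arm difference is taken to indicate a trait. It could equally come from an effect smaller than the trial can detect, or from an intervention that did not change distress.

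Second, the analysis named to follow this up answers a different question. Whether stable factors play a role in performance is a question of association (a main effect). Whether the deficit is trait-like is a question of stability over time. An arm-by-trait interaction asks for whom the arm effect differs. A trait could explain much of the variation in performance with no interaction at all, and an interaction could exist with no overall association.

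At stake is the interpretation of a null trial. A report that followed the plan could state a trait conclusion and support it with analyses that do not bear on it. For diagnosis, the interaction estimates would also be too imprecise to interpret either way.

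**Working it through.** **1. The plan's own figure.** One-way ANOVA, three groups, N = 72, f = 0.38, alpha 0.05. Noncentrality = 0.38² × 72 = 10.40; df 2 and 69; critical F = 3.13. Power = 81.3%, which reproduces the stated level of at least 80%.

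If one arm differs from two equal arms, f = 0.38 is a difference of 0.38 / √(2/9) = 0.81 SD. It can be up to 0.38 × √6 = 0.93 SD under other patterns of means. I use 0.81 SD below.

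**2. What a null leaves open.** The 95% interval for one unadjusted pairwise difference has half-width 1.995 × √(2/24) = 0.58 SD. Even a null estimate of exactly zero does not exclude arm differences of about half an SD, so non-significance alone does not separate a stable deficit from a modest effect.

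**3. What the models estimate.** With performance modelled on arm, trait and arm × trait:
- The interaction coefficients give the change in the arm effect per unit of trait. This is moderation.
- The trait coefficient in a model with arm but no interaction gives the association of trait with performance. This is the role of the stable factor.
- Neither coefficient measures stability. That needs repeated scores on the same person, such as an ICC between intake (time 1) and the end of the testing phase (time 3). According to Experimental Procedures, both laboratory tasks are given at both points.

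**4. Cell sizes for diagnosis.** Count per arm = 24 × rate, assuming the previous study's rates apply.

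| Diagnosis | With, per arm | Without, per arm | Smaller cell |
|---|---|---|---|
| Borderline personality disorder, 11.1% | 2.7 | 21.3 | 2.7 |
| Current major depression, 22.1% | 5.3 | 18.7 | 5.3 |
| Major depression, 68.3% | 16.4 | 7.6 | 7.6 |
| Generalized anxiety disorder, 40.4% | 9.7 | 14.3 | 9.7 |

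**5. Precision of a diagnosis-by-arm interaction, two arms.** SE = √(2/a + 2/b) SD, where a and b are the numbers with and without the diagnosis per arm. Detectable at 80% power = (1.997 + 0.847) × SE = 2.844 × SE (df 66). In the last column, baseline adjustment at r = 0.5 (assumed) multiplies the SE by √0.75, and pooling the two comparison arms replaces 2/a + 2/b by 1.5/a + 1.5/b.

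| Diagnosis | SE | Detectable, unadjusted | Power for 0.81 SD, unadjusted | Power for 0.81 SD, adjusted and pooled |
|---|---|---|---|---|
| Borderline | 0.919 | 2.61 SD | 14% | 21% |
| Current depression | 0.696 | 1.98 SD | 21% | 33% |
| Depression, 68.3% | 0.620 | 1.76 SD | 25% | 40% |
| Generalized anxiety | 0.588 | 1.67 SD | 27% | 44% |

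**6. Sensitivity.** If all 30 per arm were analysed, the detectable unadjusted pairwise interaction would be 1.49 to 2.33 SD, with 16-33% power for 0.81 SD. The most favourable rate for any diagnosis is 50% (12 and 12 per arm): SE = √(2/12 + 2/12) = 0.577, detectable 1.64 SD, power 28% (45% adjusted and pooled). So no other set of rates would give adequate power at 24 per arm.

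**7. The alternative on the same data.** The main effect of diagnosis uses all 72 participants: SE = √(1/(72p) + 1/(72(1−p))). For p = 0.111, 0.221, 0.404 and 0.683 this is 0.375, 0.284, 0.240 and 0.253. Multiplied by 2.842 (df 68), the detectable differences are 1.07, 0.81, 0.68 and 0.72 SD.

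**The case against.** The strongest reply is that this is a contingent, exploratory step with no claimed power. Exploring heterogeneity after a null average effect is legitimate, and low power there is unremarkable. That stands, and it limits the weight of the point. It does not repair the link between the trait conclusion and the analysis offered for it.

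The focal predictor is also unnamed. Because Aim 1 includes a distress-performance analysis, trait moderation of that relation is a possible reading. It is unstated, and it would not test trait-likeness either.

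A reader might infer more than the documents support:
- *That the fallback can neither support nor refute a trait explanation.* Too strong. A standard moderation model also carries the trait's lower-order term, so some information on association comes with it. The plan does not say that this term is the target, and it says nothing about stability.
- *That every diagnosis subgroup holds only 3 to 10 people per arm.* Not so. Major depression at 68.3% gives about 16 with the diagnosis; the 3 to 10 range describes the smaller cell of each split.
- *That sparse cells undermine the whole step.* The IRI, named first, is continuous and unaffected by cell counts.
- *That the IRI cannot serve as a stable factor because Measures and Tasks lists it among measures whose change is an exploratory outcome.* That section does not say the IRI will change, and Experimental Procedures collects it at intake, before randomisation. The intake score is a legitimate baseline variable.
- *That moderation must be run whatever the primary result, or that diagnosis must be dropped.* Both are design preferences, not corrections.

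**Conclusion.** The point holds as a mismatch between question and method. The plan attaches a trait interpretation to non-significance and follows it with an analysis whose defining term tests something else. For diagnosis, the interactions would also be very imprecise: about 1.7 to 2.6 SD needed for 80% power unadjusted, against a planned effect of about 0.81 SD. Power for an interaction of that size is about 14-27% unadjusted and 21-44% in the more favourable adjusted and pooled version.

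These figures rest on 24 analysed per arm, on the previous study's diagnosis rates carrying over to a sample that also includes untreated people, and, for the adjusted version, on an assumed baseline correlation of 0.5. The mismatch itself rests on none of these, only on reading moderation in its usual arm-by-trait sense. The primary comparison, its sample size and the data collection are unaffected.

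**What to change.** Rewrite the closing paragraph of Data Analysis & Statistical Considerations as follows.

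1. State that a non-significant arm difference alone will not be taken as evidence of trait-like deficits.
2. Examine trait-likeness by (a) the intake-to-time 3 stability of the laboratory task scores, as an ICC with 95% interval, pooled with adjustment for arm and also by arm; and (b) the main effects of intake IRI and of diagnosis on performance, adjusted for arm. With 72 participants the detectable diagnosis differences are about 0.7 to 1.1 SD.
3. Keep any moderation analysis as exploratory. Name the focal predictor, use intake values of the moderators, and report diagnosis-by-arm results as estimates with intervals, not as tests.

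The cost is wording and a few extra models on data already planned. The main downside is imprecision in single-arm ICCs: for an assumed coefficient of 0.6 with n = 24, the approximate 95% interval runs from 0.26 to 0.81. All arms, including Control, also undergo the stressor task and may receive tones between the two measurements, so the ICC describes stability under trial conditions.

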## Data & Safety Monitoring

The subjects will be fully informed of the nature of the study requirements prior to enrollment and periodically throughout the study. The subject's well-being will be continuously monitored by the study team and the Principal Investigator will report all serious adverse events in an expedited manner to the Duke University Health System (DUHS) Institutional Review Board (IRB) office and all applicable regulatory authorities in accordance with the Center's standard operating procedures.

Quality assurance. [name] will meet weekly with the Study Coordinator, assessors, and any research assistant to review any research issues that may have arisen during the past week as well as to monitor progress on subject recruitment and other research-related matters. Additional meetings are conducted on an as-needed basis.

Reporting mechanisms of AEs & SAEs to the IRB. In this study we will use the FDA's definition of adverse events (AEs) and serious adverse events (SAEs). It is not expected that any such AEs or SAEs will occur in this experiment. However, AEs and SAEs will be assessed by a trained study coordinator and discussed at the weekly research staff meetings. Any SAE will be brought to the attention of the PI as soon as possible and not longer than 24 hrs. Any SAE, will be reported to the Duke University Medical Center Institutional Review Board using the appropriate documentation within 5 days of the event. This will be the responsibility of the PI. The Duke University Medical Center Institutional Review Board will make a determination as to whether additional reporting requirements are needed.

Suicide Ideation & Risk. During the assessment day, clinical assessors will assess suicidal ideation at two points during the interview:

Time One: During the Suicide Risk and Distress Protocol (pre and post assessment)

Time Two: While assessing Major Depressive Disorder, current and past (if the subject endorses Major Depressive symptoms)

Subjects who endorse suicidal ideation but deny intent and plan will be included in the study. Subjects who are at high risk for self-harm, endorsing intent and plan, will be excluded from the study. Subjects who report a suicide attempt within the past 6 months, will also be excluded. For the subjects who are at current high risk for self-harm (i.e., intent to kill oneself is rated higher than a 4 on a 7-point scale while the assessor is going through the Suicide Risk and Distress Protocol or subject states that s/he is uncertain about being able to control suicidal impulses), assessors will complete the Suicide Assessment Worksheet and follow the instructions outlined in the Suicide Risk and Distress Protocol. This is also discussed under the minimizing risks section of this document.

Protocol violations that could represent serious or continuing noncompliance will be brought to the attention of the PI as soon as possible and not longer than 24 hrs. These violations will be reported to the Duke University Medical Center Institutional Review Board using the appropriate documentation within 5 days of notification of the PIs.

Reporting of non-study related, non-serious AEs are not reported to the IRB, and not entered on the study AE tracking log.

Non-serious AEs that are deemed study related will be reported to the PI with annual reporting and entered into the study AE tracking log. These will be reported to the IRB as needed.

Protocol deviations around study visit windows, skipped questions on self-report measures, missed therapy sessions, etc. will not be reported to the Duke IRB. Other protocol deviations will be reported to the PIs upon discovery and will then be reported to the Duke IRB within 2 weeks.

In this study, if a subject experiences an SAE or study related, non-serious AE and they are not resolved at their final study visit, because it is a minimal risk study, we do not plan to continue to follow the event past their final study visit.

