As a necessary aspect of participation in this study about emotion regulation, participants will be asked to describe and subsequently hear personally upsetting stories. This aspect of the study will be clearly delineated in the consent form and the study staff member obtaining consent will verbally describe this aspect of the study to each prospective participant. Participants are also free to discontinue the study at any time. Should a participant's discomfort become extreme and includes strong thoughts of suicide, a trained professional will be available on-site during all active study hours. Because suicidal ideation is an exclusion criterion, we do not expect this to be likely risk. We will be using the Suicide Risk/Distress Protocol along with the SCID-I to assess suicidal ideation, intent, self-harm, and date of most recent attempt at the beginning of the assessment day and at the end. In the rare event that a high rating of ideation or distress occurs, the trained study staff will work with [name] and the participant to address these suicidal thoughts and if they are deemed to be at imminent risk of suicide after the conversation, we will call 911 or obtain a commitment from the participant to go to the nearest hospital emergency room, (e.g. Duke ER). We will also use the Suicide Risk/Distress Protocol to assess ideation, intent and self-harm at pre and post the intake and laboratory sessions.

Study-related adverse and serious events are not expected but will be closely monitored and will be reported to the proper authorities according to established FDA guidelines. All information gathered in this study will be maintained in the research record.

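### Non-serious AEs judged unrelated are kept off the AE tracking log, so the log cannot support an all-cause comparison of non-serious events by arm

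*Combined protocol and SAP*

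**What the plan says.** All the recording rules are in the Data & Safety Monitoring section unless another section is named.

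- **Non-serious, judged unrelated:** "Reporting of non-study related, non-serious AEs are not reported to the IRB, and not entered on the study AE tracking log".
- **Non-serious, judged related:** "Non-serious AEs that are deemed study related will be reported to the PI with annual reporting and entered into the study AE tracking log". On onward reporting the plan adds only "These will be reported to the IRB as needed", without a criterion.
- **Serious, any attribution:** "Any SAE will be brought to the attention of the PI as soon as possible and not longer than 24 hrs", and "Any SAE, will be reported to the Duke University Medical Center Institutional Review Board using the appropriate documentation within 5 days of the event".
- **Review:** "AEs and SAEs will be assessed by a trained study coordinator and discussed at the weekly research staff meetings". No limit by relatedness is attached to this sentence.
- **Retention (Minimizing Risks):** "All information gathered in this study will be maintained in the research record".

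Neither this section nor Data Analysis & Statistical Considerations says how relatedness is decided, whether the person deciding is masked to arm, or that AEs will be tabulated or compared by arm.

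**The concern.** Whether an event is related to the study is hard to judge one participant at a time here. Participants enter with high emotion dysregulation (DERS total of at least 90), and those who report suicidal ideation without intent or plan may be enrolled. They then listen repeatedly to recordings of their own recent stressful experiences. A panic episode or a spell of worse distress afterwards could come from the existing illness or from the procedure, and the single case will often not settle which. A comparison of event counts between randomized arms could help to settle it, and that comparison needs events recorded whatever their presumed cause.

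The logging rule works the other way round: the judgement decides whether the event is recorded. The same section also says that AEs are not expected, which, without criteria, could tilt borderline calls towards unrelated. The study is meant to inform larger and longer trials, and a later team would want to know whether non-serious events differed between the arms. An event that was not entered may not be recoverable afterwards.

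**Working it through.** The documents state no AE rate, event count or harms comparison, so there is no figure of the plan's to reproduce. The check is of the text, followed by an illustration.

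**Step 1. What reaches the log, by type of event**

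| Event | On the AE tracking log? | Stated route to the PI | Stated route to the IRB |
|---|---|---|---|
| SAE, any attribution | Not stated | Within 24 hours | Within 5 days |
| Non-serious, judged related | Yes | With annual reporting | As needed |
| Non-serious, judged unrelated | No | None specific to it; weekly staff discussion covers AEs generally | No |

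The attribution filter applies to non-serious events only.

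**Step 2. What else is collected in every arm, whatever the attribution**

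- Training session (Experimental Procedures): SUDS, dissociation, Sedation Scale and PANAS-2 before and after the stressor task, skin conductance, and a question on suicidal urges at the start.
- Intake and laboratory sessions (Minimizing Risks): ideation, intent and self-harm rated before and after each.
- Testing week (Experimental Procedures): SUDS at three prompts a day, then self-report questionnaires at the end of the week.

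These allow distress, and suicide risk at sessions, to be compared by arm. They do not fully replace an event log. The suicide-risk checks are tied to sessions, and the remote week gives SUDS scores and end-of-week questionnaires, not dated events. For a discrete non-serious event in that week, the AE log is the only event record the plan describes.

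**Step 3. Illustration of the filter.** Arm size is from Data Analysis & Statistical Considerations: n = 30. The all-cause proportion with a non-serious AE, r, and the probability that an event is judged related, p, are assumptions; neither is in the documents. One event per affected participant is assumed.

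Expected events per arm = n × r: 30 × 0.20 = 6 to 30 × 0.40 = 12.

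Expected events on the log = n × r × p. With r equal in two arms, as r runs from 0.20 to 0.40:

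| p, arm A and arm B | Logged, arm A | Logged, arm B |
|---|---|---|
| 0.50 and 0.50 | 3 to 6 | 3 to 6 |
| 0.50 and 0.25 | 3 to 6 | 1.5 to 3 |
| 0.20 and 0.60 | 1.2 to 2.4 | 3.6 to 7.2 |

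In the last two rows the log shows a difference where the all-cause rates are equal. The reverse can also occur: with r = 0.20 and p = 0.50 in one arm, and r = 0.40 and p = 0.25 in the other, 30 × 0.20 × 0.50 = 3 and 30 × 0.40 × 0.25 = 3, so a twofold difference disappears. Even where p is equal, half the events are off the log at p = 0.50.

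**Step 4. Timing.** One sentence has AEs discussed weekly by the research staff. Another has related non-serious AEs go to the PI with annual reporting. The second can mean that the PI is told yearly, or that events already reviewed weekly are also gathered into a yearly report. The text does not say which.

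**The case against.** The strongest defence is proportionality. The plan calls the study minimal risk, no aim or hypothesis depends on AE counts, and with 30 per arm spontaneous AE counts would be a weaker guide to distress than the scales measured in everyone. That stands as a reason to keep the point modest. It does not remove it, because the scales do not capture discrete events in the remote week and full logging costs little.

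Four stronger readings are tempting, and the documents do not support them.

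- **That harms in general cannot be compared across arms.** SAEs are reported regardless of attribution, and distress scores and session suicide-risk ratings exist for all arms.
- **That the logging rule contradicts the promise to keep all information in the research record.** The record and the AE tracking log can be different documents, so both statements can be true. What is missing is an analysable form for the events off the log.
- **That a pattern of related events would surface only after most participants had finished.** A reader might infer this by setting the projected enrolment rate against a yearly report. It needs the PI to learn of events only once a year, on a clock starting at first enrolment. The plan states neither, and the weekly AE discussion makes that reading doubtful.
- **That attribution will differ by arm.** Nothing in the documents shows this. Step 3 shows only what would follow if it did.

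**Conclusion.** The point holds for non-serious AEs and the tracking log. By an explicit rule, an event judged unrelated is not entered, the judgement has no stated criteria or masking, and an all-cause comparison of non-serious AEs by arm cannot be made from the log. The primary analysis is untouched.

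The size cannot be fixed from the documents. On the assumptions of Step 3, with half of events judged related, 3 to 6 of 6 to 12 events per arm would be missing; any distortion between arms depends on an unequal p, which is possible but not shown. The conclusion itself rests only on the wording of the rule. The timing of PI review is a separate ambiguity that needs reconciling; it is not evidence of delayed oversight.

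**What to change.** In Data & Safety Monitoring, replace the rule for unrelated non-serious AEs with one under which every AE the team learns of is entered on the tracking log with onset date, severity, arm and a relatedness judgement made after entry. Leave IRB reporting as it is. Add a line that all logged AEs will be tabulated by arm in the final report.

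Separately, reconcile the sentence on annual reporting to the PI with the one on weekly discussion, saying whether the annual report is a summary in addition to weekly review or something else.

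The cost is a change of protocol wording, some extra log entries and one table. The small downside is that some trivial events will be logged; no reporting to the IRB is added.
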